9.1 Pre-treatment Assessments

All cases screened for the study will be captured and reason for not being recruited documented.

The following trial specific procedures will be carried out after consent:

1. Demographics recorded including gender, age, height, weight, race
2. Medical History recorded to exclude underlying pre morbid conditions, VTE history, Smoking history
3. General physical examination
4. Concomitant Medication recorded: Primarily antibiotics, noradrenaline use
5. Blood tests
 - Serum pregnancy test (for women of child bearing potential) in last 7 days
 - Baseline inflammatory parameters and routine bloods (FBC, renal, liver function and coagulation screen with fibrinogen, LDH, CRP, D dimer, ferritin)
 - Hepatitis A, B, C and HIV pre PEX (result does not need to be available before PEX)
 - Troponin T/BNP (result does not need to be available before PEX)
 - C3/4 (result does not need to be available before PEX)
 - Autoimmune screen (ANA, ENA) (result does not need to be available before PEX)
 - Factor VIII, VWF, ADAMTS-13 activity (result does not need to be available pre PEX)
 - IgG and IgM to COVID-19 (result does not need to be available before PEX)
 - PCR result for COVID-19 (result does not need to be available before PEX, see inclusion criteria for definition of probable COVID))
6. Respiratory parameters: SaO₂, RR
 - PaO₂, FiO₂
 - Method of assisted ventilation eg HDNOHFNO, CPAP
 - P:F ratio
 - CXR/ CT/HRCT : if undertaken as part of routine clinical care
7. Cardiac investigations
 - ECG (result does not need to be available before PEX)

- Echocardiography (if available within 48 hours of enrolment to study)

The results from the following routine procedures may be used:

Blood test results within 48 hours of enrolment

PCR result for COVID-19 within past 14 days (result does not need to be available before PEX, see inclusion criteria for definition of probable COVID)

Pregnancy test within 7 days

Where routine results are not available, the procedure(s) will be carried out at screening after consent.

All pre-treatment procedures will be carried out as specified in the schedule of assessments (**appendix 2**).

9.2 Registration / Randomisation Procedures

Participant randomisation will be undertaken remotely at sites using central randomisation system developed by Sealed Envelope.

Following participant consent, and confirmation of eligibility (see section 8.1 for pre-treatment assessments) the registration/randomisation procedure described below will be carried out.

Participants are considered to be enrolled into the trial following: consent, pre-treatment assessments (see section 8.1), confirmation of eligibility, completion of the registration/randomisation process, allocation of the participant trial number and treatment by the central coordinating team/remote system.

Patients will be randomized to either PEX+SOC or SOC in a 1:1 ratio using block randomization with varying blocks sizes.

Randomisation will be carried out by the online randomisation system provided by commercial company Sealed Envelope . This will be accessed by a designated member of staff who will communicate the treatment allocation to the clinical team.

9.3 Treatment Schedule

IMP = OctaplasLG, Octapharma, Limited UK: 40mls/Kg intravenously via plasmapheresis

Licensed for therapeutic plasma exchange

OctaplasLG via plasmapheresis

Intravenous infusion of Octaplas to the nearest litre (which in the majority of patients will be 3 litres) through a Cobe Spectra apheresis machine over 2-3 hour, with removal of a comparable volume of plasma once daily for 5 days.

Single volume PEX capped at 3 litres if <100Kg and 4 litres if >100Kg.

PEX will be given for a minimum of once a day for 5 days, but the course can be repeated depending on patient's response, based on a reassessment on D5 to D7. The 5 day PEX will be repeated in patients showing clinical and biochemical improvement but persistent pro-thrombotic phenotype following the initial 5-day block

The Cobe Spectra is the preferred technology for plasma exchange, but plasma exchange may be performed on haemofilters.

The following drugs are considered to be non-investigational medicinal products (NIMPs) in this Trial:

Medications used during plasma exchange (NIMPs)

The following drugs are standard adjunctive treatment during plasma exchange which may be given during PEX

- Calcium replacement either oral or iv
- Hydrocortisone 100mg intravenously
- Chlorpheniramine 10mg intravenously (or 4mg orally)
- Paracetamol 1g orally.

All medications need to be documented on the CRF and source document.

These are NIMPS as they are not treating the disease but are used to potentially reduce any infusional side effects of plasma exchange.

Intermediate dose LMWH for all patients within the study: <100Kg 40mg BD enoxaparin (or equivalent LMWH), > 100Kg, 60mg BD Enoxaparin

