- B. Citrate reactions: Some patients treated with PEX present with features of hypocalcaemia (fatigue, paraesthesia, tremor, and hypocalcemia). This is treated with calcium boluses, but offset by a calcium infusion throughout PEX.
- C. Risk of viral transmission: Standard measures to prevent infections resulting from the use of medical products prepared from human blood or plasma include selection of donors, screening of individual donations and plasma pool for specific markers of infection and the inclusion of effective manufacturing steps for the inactivation/removal of viruses. When medicinal products prepared from human blood or plasma are administered, the possibility of transmitting infective agents cannot be totally excluded. However Octaplas LG undergoes a number of additional pathogen inactivation steps and is considered very safe.

The table below summarises the risks, frequencies and mitigations of the IMP(s) and NIMP(s) (delete NIMP if it is not applicable)

Name of IMP(s) / NIMP	Potential risk	Risk Frequency	Risk Management
Octaplas	-Reactions to plasma - -Pathogen transmission	-Severe reactions- grade 4- anaphylaxis <1% -Due to nanofiltration and S/D processing, this is the safest and most effective plasma available	-Any reactions treated with antihistamine, paracetamol and /or hydrocortisone -PEX would be stopped if any severe reaction/anaphylaxis -routine viruses are checked pre PEX.
PEX procedure	Citrate toxicity	10-20% of procedures	IV calcium is run during PEX and added boluses given if required

Vascath insertion	Infection, bleeding, thrombosis	Approx. 10%	Lines are changed weekly to reduce infection, intermediate LMWH given, reducing thrombosis. Bleeding rare as lines inserted by USS
-------------------	---------------------------------	-------------	--

Type A = No higher than the risk of standard medical care

5 Objectives

The rationale of this study is to compare outcomes of patients receiving PEX to those who do not. We hope to ascertain if PEX provides a clinical benefit to expand its use nationally and internationally, as there is currently no treatment which improves the morbidity and mortality of patients with severe COVID-19.

Primary objectives:

To compare reduction in inflammatory markers between Plasma Exchange (PEX) and control groups in patients with severe COVID

Secondary objectives:

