The Principal Investigator (PI) has overall responsibility for the informed consent of participants at their site and will ensure that any person delegated responsibility to participate in the informed consent process is duly authorised, trained, and competent to participate according to the ethically approved protocol, principles of Good Clinical Practice (GCP), and Declaration of Helsinki. If delegation of consent occurs then details will be provided in the site delegation log.

The right of a participant to refuse participation without giving reasons will be respected. The participant will remain free to withdraw at any time from the study without giving reasons and

without prejudicing his / her further treatment, and will be provided with a contact point where he / she may obtain further information about the study.

Participants will be severely ill at the time of eligibility (non-invasive ventilation or intubated on mechanical ventilation and sedation), such that the Medicines for Human Use (Clinical Trials) Regulations provides guidance. Those who are not sedated and intubated will have been through a psychologically anxiety provoking event and will often be extremely distressed due to severe difficulty breathing and hypoxia. As such they may be unable to fully comprehend an important consideration when the intervention under investigation is time sensitive. The PI is responsible for ensuring that all vulnerable participants are protected and participate voluntarily in an environment free from coercion or undue influence.

A legal representative can be asked to give consent on behalf of an adult lacking capacity to do so themselves.

Those who are able to act as a legal representative in Clinical Trials of Investigational Medicinal Products (CTIMPs), in England and Wales are:

- Personal legal representative i.e. a person not connected with the conduct of the trial who is suitable to act as the legal representative by virtue of their relationship with the adult, and is available and willing to do so. If one is not available:
- Professional legal representative i.e. a doctor responsible for the medical treatment of the adult if they are independent of the study, or a person nominated by the healthcare provider.

Additional consent provisions for collection and use of participant data and biological specimens in ancillary studies:

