9.5 Laboratory Assessments and Procedures

Local laboratories

The following tests will be carried out at Local Laboratories:

Laboratory test	Parameters
BLOOD	
Haematology	leukocytes, erythrocytes, haemoglobin, haematocrit, mean corpuscular volume (MCV), mean corpuscular haemoglobin (MCH), platelets, neutrophils, eosinophils, basophils, lymphocytes, monocytes;

Serum chemistry	alanine transaminase (ALT), alkaline phosphatase, total bilirubin, creatinine, urea, potassium, sodium, albumin
Clotting screen	Prothrombin time, activated partial thromboplastin time, claus fibrinogen,
Inflammatory markers	C reactive protein (CRP), lactate dehydrogenase (LDH), D dimer, ferritin
Pregnancy test	Serum bhCG
Virology test	Covid 19 PCR, Covid 19 IgM and IgG, Hepatitis-B-virus surface antigen (HBsAg), anti-hepatitis C virus (anti-HCV) antibodies, immunodeficiency virus 1 and 2 (anti-HIV1/2) antibodies,
Cardiac markers	Troponin, BNP
Procoagulant markers	Factor VIII, VWF, ADAMTS-13 activity
Autoimmune screen	C3/C4 ANA ENA
Multiplex inflammatory markers	cytokines including interleukins, interferons, and vascular markers of endothelial injury 'cytokine storm'

Central laboratories

No central laboratory

Translational Research Samples

Citrated plasma and serum samples can be used for COVID-19 related translational research as authorised by the trial team. All data and samples will be available for COVID19 related research, to improve the understanding of the condition. This may be within the team/trust or in collaboration with external researchers. All data/samples in the latter situation will be anonymised.

The samples will be spun and stored in Special Coagulation Laboratory, [name]

Any analysis of samples needs a formal risk assessment re aerosol risk when spinning or as part of analysis and will only be undertaken following health and safety sign off within HSL/UCLH/UCL.

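### Sections 4 and 9.3 disagree on whether calcium cover during plasma exchange is routine IV or optional oral or IV, and no calcium measurement is specified, so the citrate rate cannot be reported reliably

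*Combined protocol and SAP*

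**What the plan says.** Section 4 (Assessment and management of risk) deals with citrate twice. Item 2B, on citrate reactions, says of hypocalcaemia: "This is treated with calcium boluses, but offset by a calcium infusion throughout PEX". The risk table in the same section puts citrate toxicity at "10-20% of procedures" and gives as its management: "IV calcium is run during PEX and added boluses given if required".

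Section 9.3 (Treatment Schedule) lists the non-investigational products for use with PEX. It describes them as standard adjuncts that may be given, and the calcium entry reads "Calcium replacement either oral or iv". It also asks for all medications to be documented on the CRF and source document.

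Section 9.5 itemises serum chemistry as "alanine transaminase (ALT), alkaline phosphatase, total bilirubin, creatinine, urea, potassium, sodium, albumin". Calcium is not among the eight analytes. It is not named in the pre-treatment bloods (9.1) or the visit schedule (9.4.1), and Appendix 3 has only a general biochemistry row.

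Section 8.3 describes participants at eligibility as severely ill: "non-invasive ventilation or intubated on mechanical ventilation and sedation".

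**The concern.** The section 4 risk assessment depends on a specific mitigation, and the treatment schedule does not require it. Staff who give oral calcium only, or none, comply with 9.3 and depart from section 4. The risk table also does not say which calcium practice its stated citrate frequency assumes.

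The second part is measurement. Section 4 lists fatigue, paraesthesia, tremor and hypocalcaemia as the features of a citrate reaction. A sedated participant cannot report fatigue or paraesthesia, and no scheduled calcium value stands behind the symptoms. What is at stake is patient safety during the exchange, and whether the trial can give a dependable citrate rate to set against the one it states.

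**Working it through.** **Step 1: the calcium statements side by side.**

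| | Section 4, text | Section 4, risk table | Section 9.3 |
|---|---|---|---|
| Status | Infusion throughout PEX | Run during PEX | Permitted, not required |
| Route | Infusion, with boluses as treatment | IV, with boluses if required | Oral or IV |

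IV calcium run during PEX satisfies all three columns. Oral calcium alone, or no calcium, satisfies only the last. The statements therefore differ on status and on route, and the looser one sits in the treatment schedule.

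**Step 2: is a calcium value specified anywhere?** Section 9.5 itemises serum chemistry without calcium; 9.1 and 9.4.1 do not name it; the biochemistry row in Appendix 3 is not broken down. Since 9.5 does break serum chemistry down, reading calcium into that row would be a guess.

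**Step 3: what do the existing records capture?**
- Adverse events: section 10.1 counts a change in laboratory data as an adverse event, 10.2 records events from consent, and citrate reactions are not on the 10.5 list of COVID-19 events exempt from capture. Without a scheduled calcium value, though, this route depends on a reaction being noticed.
- PEX reactions graded 1-4 (9.4.1): section 4 uses these grades for reactions to plasma. Citrate is a separate item there and has no grades.
- Adjunct drugs on the CRF (9.3): under section 4 calcium is routine, so a record of it does not mark an event; under 9.3 it might. The entry cannot be interpreted until the sections agree.

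**Step 4: expected burden.** The protocol gives no numerator, denominator or source for 10-20%, so the figure cannot be reproduced and is taken as stated. Section 12.2.1 and the synopsis give 20 to 40 patients in total, which at 1:1 is 10 to 20 in the PEX arm. Section 9.3 gives at least 5 exchanges each.
- 10 patients × 5 = 50 exchanges; 50 × 0.10 = 5 and 50 × 0.20 = 10 events.
- 20 patients × 5 = 100 exchanges; 100 × 0.10 = 10 and 100 × 0.20 = 20 events.

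If exchanges are assumed independent, the chance that a patient has at least one event in k exchanges is 1 − (1 − p)^k:
- k = 5: 1 − 0.9^5 = 0.41 and 1 − 0.8^5 = 0.67.
- k = 10 (only patients given a second block): 1 − 0.9^10 = 0.65 and 1 − 0.8^10 = 0.89.

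Clustering of events within patients would lower these proportions but leave the expected counts unchanged.

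**The case against.** The strongest reply is that this is a stricter and a looser statement, not two incompatible ones. The 9.3 list classifies adjuncts as non-investigational and forbids nothing in section 4. This stands: a reader might infer that the two sections cannot both be followed, but IV calcium run during PEX meets both. What remains is that 9.3 alone does not secure the mitigation.

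A reader might also infer that citrate toxicity goes unmeasured, or that its rate cannot be reported at all. The documents do not support that, because adverse event collection, graded PEX reactions and drug recording all exist. Nor does section 4 make symptoms the method of detection: it names hypocalcaemia beside them, sets no detection method, and gives no trigger for a bolus. The gap is a specified calcium value and a citrate-specific record.

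Calling citrate the most frequent PEX toxicity would likewise go too far. It has the highest frequency listed, but the line-complication figure of about 10% has no denominator, and plasma reactions of grades 1-3 have no frequency.

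Section 9.7 says PEX and the adjuncts are given by trained apheresis staff under a Trust protocol. That document is not available here and may cover calcium, including its measurement. It could narrow the practical gap, but 9.7 does not say whether section 4 or 9.3 governs.

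Finally, adding calcium to an untimed daily sample would not meet the need, because an exchange lasts 2-3 hours and such a sample could miss the fall. That is correct, and the fix below allows for it.

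**Conclusion.** The point holds as one of safety and conduct. Section 4 and section 9.3 differ on whether calcium is routine or optional and on its route, so treatment within 9.3 can leave out the stated mitigation. No calcium measurement is specified, and the existing records do not isolate citrate reactions, so their rate cannot be reported reliably.

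The size, at the protocol's own unsourced rate, is 5-10 expected events in first blocks with 10 PEX patients and 10-20 with 20. A reader might take these as events that would be missed or mishandled. They are not: they show how much toxicity the protocol itself expects, and the documents give no basis for the share that would go unrecognised. The per-patient percentages rest further on independence between exchanges.

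The primary outcome, its analysis and the power are untouched. No view is taken on which calcium statement is right.

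**What to change.** 1. Reconcile section 4 (text and risk table) with 9.3 so that one statement on calcium applies. Its content is the sponsor's decision.
2. Add calcium to the serum chemistry list in 9.5 and to Appendix 3. Run it on the serum that 9.4.1 already draws before and after PEX, not on an untimed daily sample. Two samples bracket the exchange, though a fall that recovers before the second could still be missed.
3. Record on the CRF, for each exchange, the calcium values and whether a citrate reaction occurred. Recording of any calcium given is already required by 9.3.

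The cost is a wording amendment, a CRF entry and one added assay per sample: 2 × 50 = 100 to 2 × 100 = 200 assays over first blocks. No extra venepuncture is needed, but 9.4.1 and 9.5 send these samples to be spun and stored, so some of the serum would have to be routed for the calcium test.

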Lodigiani C ¹²	Ward: 326 (84%) ICU: 62 (16%)	75% of ward patients 100% of ICU patients	n=20 (6.4%) n=8 (16.7%)	n=4 (1.3%) n=1 (2.1%)	n=2 (4.2%) n=8 (2.5%)	n=1 (1.9%) n=1 (6.3%)
Zhang ¹⁵	Non COVID-19	281 ICU patients	(9.6%)	n=24	n=1	

Table 3: Thromboembolic complications in patients with COVID-19

The UK already adopts a policy of thromboprophylaxis (after VTE risk assessment) in all hospital inpatients to prevent thrombosis. The risk of thrombosis is compounded in sick patients in HDU/ICU settings by immobility, co-morbidities, (arterial disease, diabetes) body weight, acute inflammatory response and associated therapies e.g. steroids.

UCLH has the largest international cohort of patients with thrombotic thrombocytopenic purpura (TTP) and other thrombotic microangiopathies. Their presentation is acute, associated with anaemia, thrombocytopenia and end organ damage, primarily, the heart, brain and kidney. The respiratory system is not affected in TTP. Other thrombotic microangiopathies (TMA) have variable organ involvement eg HUS does have pulmonary disease. The diagnosis of TMA is primarily clinical, but may be defined by histology. The mainstay of treatment is plasma exchange, using octaplas. The rationale for Octaplas is its safety profile and reduced high molecular weight forms of von Willebrand factor. The role of plasma exchange (PEX) is delivery of high volumes of plasma, replenishing deficient factors e.g. ADAMTS 13, natural anticoagulants/coagulation factors, and complement proteins, leading to normalization of routine laboratory parameters, in particular, FBC, renal function, and LDH. Furthermore PEX has been demonstrated to reduce inflammatory markers, which are extremely high at presentation in TMAs (comparable to levels seen in COVID19) and subsequently ameliorated following PEX. PEX is standard of care for thrombotic microangiopathies, which severe COVID-19 infection appears to mimic.

3.1 Hypothesis:

Patients with COVID-19 have elevated procoagulant factors including VWF and factor VIII secondary to direct endothelial activation. This is associated with an exaggerated pro-inflammatory immune response and microvascular thrombosis; resulting in multi-organ dysfunction and eventually death. PEX will improve coagulopathy, as measured by VWF:ADAMTS 13 ratio and D Dimers, with an associated reduction in inflammation, organ-related microthrombosis, and ventilatory support.

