9.4 Subsequent assessments and procedures

9.4.1 Visit schedule and assessments

A schedule of all trial assessments and procedures is set-out in **Appendix 3**.

Day 1- 5

- eligibility check pre PEX if randomised to PEX
- Vitals pre and post PEX (temperature, blood pressure, pulse, respiratory rate and oxygen saturation level) or once daily
- Plasma exchange if randomised to PEX
- assessment of compliance with PEX
- general physical examination
- recording of relevant concomitant medications eg start stop dates of antibiotics, noradrenaline
- Daily routine bloods (FBC, renal, liver function and coagulation screen with fibrinogen)
- Inflammatory markers on D1,D3 &D5 (LDH, CRP, D dimer, ferritin)
- Citrated plasma and serum samples pre and post PEX, or daily for those randomised to SOC to save for VWD screen, ADAMTS13 activity, COVID-19 serology, and multiplex inflammatory markers related to ILs cytokines, interferons, and vascular markers of endothelial injury. Spare samples can be used for COVID-19 related research as authorised by the trial team
- Respiratory parameters: Oxygen requirement, respiratory rate, type of ventilator support-as part of standard of care assessment
- Echocardiogram on D1
- Troponin and BNP on D1
- adverse event collection
- Reactions to Plasma exchange: graded 1-4
- Complications related to central vascath
- Need for antibiotics
- Deterioration requiring ventilation
- Arterial or venous thrombotic event

Reassessment (Day 5-7)

Review of clinical and laboratory parameters by trial team. Consideration of further 5 day block of PEX if clinical and biochemical improvement following initial 5-day block but persistent pro-thrombotic phenotype

*If a patient has a second 5 days of PEX started-follow instructions for day 1-5 above

Follow up Day 6 - 28*

- Vitals (temperature, blood pressure, pulse, respiratory rate)
- general physical examination-weekly
- recording of concomitant medications-related to antibiotics, new cardiac medication, but not all the routine medicines re SOC and not including PRN medications.
- Daily routine bloods (FBC, renal, liver function and coagulation screen with fibrinogen)
- Inflammatory markers, at least 3 x/week (LDH, CRP, D dimer, ferritin)

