12.1.2 Secondary outcomes

1. Number of patients requiring mechanical ventilation who required only supplemental O₂/CPAP at study entry. This will be captured throughout the period of the study, by review of the oxygen requirements and ventilatory support required throughout the study (O₂ requirement or PaO₂:FiO₂ (P:F ratio) sequentially)
2. 50% decrease in VWFAg/ADAMTS 13 activity ratio from baseline to end of PEX.
3. Prevent deterioration in myocardial function on ECHO/ cardiac parameters -monitoring of cardiac function through echocardiogram and/ or BNP and Troponin levels throughout study period
4. Clinical thrombotic events documented by imaging either venous DVT/PE, or arterial thrombus (cardiac, neurological and peripheral vascular) throughout the study period
5. Incidence of acute kidney injury as defined by KDIGO criteria throughout study period
6. Mortality at 28 days

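### Do the differing medication-recording rules after Day 5 call for a change to the plan?

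*Combined protocol and SAP*

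**What the plan says.** Medication recording is described in several places in the combined protocol and SAP.

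- Section 7.3 has concomitant medication recorded in the notes or the case report form (CRF), with no limit by drug or period.
- Section 9.1 (baseline) and section 9.4.1 (Day 1-5) mention antibiotics and noradrenaline, worded as main items or examples.
- Section 9.3 lists drugs that may accompany PEX, among them "Hydrocortisone 100mg intravenously", and then says "All medications need to be documented on the CRF and source document". After that, outside the list, comes "Intermediate dose LMWH for all patients within the study".
- Section 9.4.1, Day 6-28, covers antibiotics and new cardiac drugs, "but not all the routine medicines re SOC and not including PRN medications". The footnote marker on its heading leads to: "If a patient has a second 5 days of PEX started-follow instructions for day 1-5 above".
- Appendix 2 has a medication review at every visit. Appendix 3 has a medication row marked on every scheduled day to Day 28, with antibiotics and noradrenaline as examples. Neither is split by arm.

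On relevance, section 3 includes among the factors that compound thrombosis risk in HDU/ICU patients "acute inflammatory response and associated therapies e.g. steroids". The section 4 risk table, in the row on catheter insertion, has "intermediate LMWH given, reducing thrombosis". Section 12.1.2 makes thrombosis the fourth secondary outcome: "Clinical thrombotic events documented by imaging either venous DVT/PE, or arterial thrombus (cardiac, neurological and peripheral vascular) throughout the study period".

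**The concern.** Three things look wrong on a first reading. An instruction to document every drug appears to clash with one that leaves some out. The second-block footnote applies only to patients receiving PEX, so on the same calendar days the two arms can be under different recording lists. And steroids given as standard care and low-molecular-weight heparin (LMWH), which the protocol itself connects with thrombosis, are on none of the recording lists, although treatment is unblinded and standard care is left to the clinicians.

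At stake would be a by-arm summary of co-medication after Day 5. It could show a difference that the recording rule created, or hide a real one, just where a reader might want to set the thrombosis result against steroid and heparin use.

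**Working it through.** The plan gives no figure on this point, so there is none to reproduce. The check is a comparison of the texts plus some day counts.

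**1. The recording statements side by side**

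| Place | Period | Drugs named | Left out |
|---|---|---|---|
| 7.3 | not limited | none | nothing; notes or CRF |
| 9.1 | baseline | antibiotics, noradrenaline (main items) | nothing |
| 9.3 sentence | with PEX | calcium, hydrocortisone, chlorpheniramine, paracetamol | not applicable |
| 9.4.1 Day 1-5 | Days 1-5; any second block | antibiotics, noradrenaline (examples of relevant drugs) | nothing |
| 9.4.1 Day 6-28 | otherwise | antibiotics, new cardiac drugs | PRN; some routine standard-care drugs |
| Appendix 2 | all visits | none | nothing |
| Appendix 3 | scheduled days to Day 28 | antibiotics, noradrenaline (examples) | nothing |

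Of the five recording lists (9.1, the two in 9.4.1, and the two appendices), none names LMWH or standard-care steroids. Only one, Day 6-28, leaves anything out.

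**2. Scope of the 9.3 sentence.** It follows the four PEX adjuncts directly, and the next sentence explains why these drugs are non-investigational products. The adjuncts are given with PEX, and a second block is under the Day 1-5 list. On this reading there is no day on which 9.3 and the Day 6-28 list give opposite orders. A conflict arises only if the sentence covers every drug in the trial. In that case it already puts heparin and standard-care steroids on the CRF, and the omission largely goes away. The clash and the omission from 9.3 therefore do not hold together.

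**3. What remains after Day 5.** Section 7.3 is met by an entry in the notes. Appendix 3 gives noradrenaline as an example to Day 28 and the Day 6-28 list does not name it, though a new start could count as a new cardiac drug. This is a mild mismatch between a schedule row and its detailed text.

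**4. Length of the arm difference.** Days 6-28 are 28 - 6 + 1 = 23 days, or 23/28 = 82% of follow-up. A second block takes 5 of them: 5/23 = 22% in a PEX patient who has one, against 0/23 in a control patient.

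**5. Size of a recording artefact.** Let u be the share of each arm with a start, change or PRN dose of such a drug on those 5 days, and r the share of PEX patients with a second block, unrelated to u. Let a and b be the chances that it is recorded under the Day 1-5 and Day 6-28 lists. Then

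- control arm: u × b
- PEX arm: r × u × a + (1 - r) × u × b
- difference: r × u × (a - b)

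The documents give none of the four. In the all-or-none case (a = 1, b = 0) the difference runs from 0.10 × 0.25 = 2.5 points to 0.50 × 0.50 = 25 points over r = 10-50% and u = 25-50%. The top corner, at 20 per arm, is 5/20 against 0/20 (Fisher p = 0.047). But the Day 1-5 list asks only for relevant drugs, so a need not be 1, and the Day 6-28 list excuses some routine drugs, not all, so b need not be 0 for these. With a = b the difference is zero. The large figures come from the assumed inputs, and the plan contains no test of such a table.

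**6. Use in the planned analyses.** Section 12.4.2 tests marker response by chi-squared. Section 12.4.3 compares the secondary outcomes and allows adjusted analyses without naming covariates. Section 12.4.4 deals with missing data. None specifies medication. Thrombotic events have their own line in both 9.4.1 lists and are documented by imaging, so counting them does not depend on medication records.

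**The case for a change.** The best case for a change is that the text is loose on either reading of 9.3. Read broadly, it clashes with the Day 6-28 list. Read narrowly, hydrocortisone given with PEX must be documented, while nothing expressly secures a steroid given as standard care, or heparin. Words such as relevant permit recording without requiring it. One rule for both arms would need a few CRF fields in at most 40 patients, and in an unblinded trial a reader may fairly ask about co-medication.

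Part of this stands. The footnote has no control-arm counterpart, the Day 6-28 list and Appendix 3 are not aligned, and the two drug groups are not named. A clarifying sentence would do no harm.

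Its weight is small, however. LMWH is set for all patients in both arms, so what might go unrecorded is mainly later changes. The section 4 remark on heparin concerns the catheter, and the section 3 remark on steroids is general background. Section 11.2 places all data at the coordinating hospital on its electronic record, so an item missing from the CRF can be recovered. An analyst who wanted a co-medication table would draw it from that record by the same rule in both arms. Limiting follow-up recording to selected drugs in severely ill inpatients is a fair trade-off against data-entry burden.

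**Conclusion.** No change to the plan is needed. The apparent contradiction between 9.3 and 9.4.1 comes from reading one sentence outside its list. What is left is a data-capture looseness: recording may differ by arm on 5 of 23 days (22%) for PEX patients who have a second block, and two drug groups are not named. It alters no planned result. The primary test uses no medication data, thrombosis is ascertained separately, and the comparison of PEX with its adjuncts plus standard care against standard care alone remains valid as randomised.

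This rests on two assumptions. The trial stays at the single site given in the synopsis, or any further site keeps retrievable medical records. And no adjusted analysis under 12.4.3 uses drug exposure after randomisation as a covariate; the plan proposes none.
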